5.4 Treatment blinding

Treatment code will be open to patients, investigator staff, and persons performing the assessments. The clinical trial team (e.g. Clinical Trial Lead, Clinical trial Manager, Medical Lead, Trial Statistician) will be blinded to the identity of the treatment from the time of randomization until database lock. Randomization data will be kept strictly confidential until the time of unblinding, and will not be accessible by anyone else involved in the study with the exception of those mentioned in the Safety Manual.

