5.5.5 Permitted dose adjustments and interruptions of study treatment

Systolic Blood Pressure (SBP) has to be ≥ 125 mmHg for the patient to be eligible, and then ≥ 125 mmHg during the screening period, in particular at the end of the screening period just before calling the IRT for randomization. In many centers, continuous cardiac monitoring will probably be applied and this will keep the site informed about SBP values.

Considering the high fluctuation of blood pressure in patients with decompensated HF, especially because the patient might be under the effect of nitrates (even at low dose) and diuretics, it is advised to minimize the time windows between the end of screening, the IRT call and start of the serelaxin infusion.

In practice:

- BP has to be measured at the end of screening and SBP must be ≥ 125 mmHg before calling the IRT. Once the patient is randomized, the study drug should be prepared promptly (if the patient is in the serelaxin group).
- Just before the immediate start of study drug infusion, SBP must be assessed again. During that interval between randomization and infusion start, sometime will elapse (30 to 60 minutes in most cases) and BP may fluctuate.
 - It is not required that pre-infusion SBP be ≥ 125 mmHg (SBP ≥ 125 mmHg is an inclusion criterion and matters only up to randomization)
 - If at the immediate start of study drug infusion, SBP is below 100 mmHg (SBP < 100 mmHg), serelaxin should not be started, neither now nor later. The patient will remain in the study up to 30 days but will not have received serelaxin
 - If a blood pressure fall has occurred since randomization but SBP is still ≥ 100 mmHg, the decision to start or not the infusion remains at the discretion of the investigator, based on the hemodynamic context of the patient (i.e. previous hemodynamic stability, DBP, concomitant medications, medical response to IV furosemide/diuretics, etc.).

Of note, there is no mandatory time window between randomization and start of the study drug infusion. This time span should be kept as short as possible. For microbiological reasons, there is a maximum time of 4 hours allowed between preparation (mixing) of the study drug and infusion start.

If at any time during the study drug infusion, the subject's systolic blood pressure decreases by >40 mm Hg from just before the study drug infusion but is ≥ 100 mmHg in two consecutive measurements 15 min apart, the serelaxin infusion rate will be decreased by 50% for the

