5. STATISTICAL METHODOLOGY

5.1. GENERAL METHODOLOGY

Data will be analysed according to the data analysis Section 9 of the study protocol.

All statistical tables, listings, figures and analyses will be produced using SAS® release 9.4 (64-bit) or later (SAS Institute Inc., Cary NC, USA).

The data from all countries and all sites will be pooled and summarized. Continuous data will be summarized by the mean, standard deviation (SD), median, first and third quartiles,

	Statistical Analysis Plan
	Sponsor: NOVARTIS Protocol number: CRLX030A3301

minimum and maximum. Categorical data will be presented by absolute and relative frequencies (n and %) or contingency tables.

All nominal time points will be used for analysis; actual assessment times will not be used to reclassify the time point at which a measure was taken. Time-to-event analyses will be based on actual dates (times) reported.

Subjects will be included in each efficacy analysis based on available assessments, after the data handling conventions have been applied. The prevalence approach (i.e., no imputation of missing data), if not differently indicated, will be applied.

Unless stated otherwise, two-sided p-values < 0.05 will be considered statistically significant. No formal interim efficacy analysis will be performed and therefore no statistical adjustment of alpha level will be required.

Visit, baseline and post baseline definitions

Screening phase: The screening phase is defined as the period prior to randomization. After obtaining written informed consent, the subject will be evaluated for eligibility to participate in the study.

Baseline definition for efficacy and safety measurements: Baseline date and time is defined as the date and time of initiation of study drug for the serelaxin group, or date and time of randomization for the SOC group. Of note, the randomization date and time will be used as the reference date and time for all time to event analysis.

Post-baseline phase for efficacy and safety measurements: The post-baseline phase begins at the date and time of initiation of study drug administration for the serelaxin group, or the date and time of randomization for the SOC group, and ends with the last study assessment/last follow-up or the death of subject. For subjects who did not receive study drug, the phase begins at the time of randomization.

Patient disposition and analysis population

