Each sign or symptom of HF, collected in “Physician Assessment of Signs and Symptoms of Heart Failure” eCRF page, will be analysed separately. The event is defined as ≥ 1 point improvement from baseline. The time to being a responder will be computed as the number of hours from randomization to the date and time of the first assessment at which a ≥ 1 point improvement from baseline is detected plus 1 minute. Subjects without an event will be censored at the earlier of the last post-baseline assessment of signs and symptoms of HF or 336 hours (i.e., 14 days) after randomization. Subjects without any information after baseline (i.e., randomization) will be considered censored at 1 minute. In case of missing time of assessment of signs and symptoms of heart failure then 00:00 will be imputed. The analysis will be performed excluding subjects with the following signs and symptoms at baseline: ‘None’ for Dyspnea on exertion and Orthopnea; ‘0’ for Edema; ‘No rales’ for Rales; ‘<6 cm’ or ‘Not evaluable’ for Jugular venous pulse, ‘No’ for Body weight increase.

Table 5.2-6: Censoring and time rules

	Statistical Analysis Plan
	Sponsor: NOVARTIS
	Protocol number: CRLX030A3301

	Status	Time
At least one (≥ 1) point improvement occurred and:		
Difference between date and time of first occurrence improvement (i.e., date and time of physician assessment where improvement was assessed) and date and time of randomization +1 minute > 336 hours	Censored	336h
Difference between date and time of first occurrence improvement (i.e., date and time of physician assessment where improvement was assessed) and date and time of randomization +1 minute ≤ 336 hours	Event	Calculated difference
No improvement occurred and		
Difference between date and time of last available physician assessment and date and time of randomization +1 minute > 336 hours	Censored	336h
Difference between date and time of last available physician assessment and date and time of randomization +1 minute ≤ 336 hours	Censored	Calculated difference

Moreover, summary statistics for data about physician assessment of signs and symptoms of HF will be provided at each assessment time point by treatment group. Absolute and relative frequencies of patients reporting each sign/symptom will be provided. Percentages will be computed considering patients with non-missing information at each assessment time point and by each type of sign and symptom.

Renal deterioration

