EQ-5D-5L health states will be converted into a single index value using UK as the reference country for all countries. Studies that derive values sets and procedure for the index computation are under development in a number of countries; the most updated SAS code from the EQ Executive Office will be applied (i.e. reference set for UK updated on January 2016 obtained from *“Devlin, N., Shah, K., Feng, Y., Mulhern, B. and van Hout, B., 2016. Valuing Health-Related Quality of Life: An EQ-5D-5L Value Set for England. OHE Research Paper 16/01. London: Office of Health Economics”*). Summary statistics will be provided for the index value at each visit by treatment group.

To compare treatment groups in quality of life change from baseline (i.e., randomization), a mixed model for repeated measures will be fitted to overall health index score absolute changes from baseline (score at time of assessment - score at baseline), and considering treatment, visit and treatment by visit as factors, and value at baseline as covariate.

If data do not respect normality assumption, a rank transformation will be applied.

The questionnaire/scale completion status will be summarised descriptively by treatment group at each visit.

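### SAP 5.1 sets the efficacy baseline at infusion start on serelaxin but at randomization on SOC; this permits, on serelaxin only, a contemporaneous symptom or EQ-5D baseline taken after open allocation, and it conflicts with other baseline definitions in the plan

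*SAP*

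**What the plan says.** SAP 5.1 defines baseline for efficacy and safety measurements together. On serelaxin: "Baseline date and time is defined as the date and time of initiation of study drug for the serelaxin group". On the other arm: "or date and time of randomization for the SOC group". It adds that "the randomization date and time will be used as the reference date and time for all time to event analysis". The post-baseline phase starts at the same arm-specific moments, except that patients who received no study drug start it at randomization. The same section also says: "All nominal time points will be used for analysis; actual assessment times will not be used to reclassify the time point". Time-to-event analyses are exempt from that and use actual dates and times.

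SAP 5.2 uses baseline values in two efficacy areas. In the sign/symptom response analyses, baseline fixes the event (an improvement of at least 1 point) and also decides who is analysed: "The analysis will be performed excluding subjects with the following signs and symptoms at baseline". In the EQ-5D repeated-measures model, baseline is both the reference for change and a covariate, and there it is glossed as randomization: "in quality of life change from baseline (i.e., randomization".

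Protocol 5.4 states: "Treatment code will be open to patients, investigator staff, and persons performing the assessments". Protocol 5.5.5 expects 30 to 60 minutes between randomization and infusion in most cases, and then says: "Of note, there is no mandatory time window between randomization and start of the study drug infusion".

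**The concern.** In a randomized comparison, a baseline should be fixed before allocation can influence it, and in the same way in both arms. Here the serelaxin reference point is a post-randomization event. A clinician's grading of dyspnea or rales, or a patient's own EQ-5D rating, made in the gap with allocation known, falls before baseline on serelaxin and after baseline on SOC. These are subjective measures.

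Three things would then differ by arm: the value from which change is measured, the set of patients who enter each symptom analysis, and the EQ-5D covariate. In addition, the SAP gives a programmer more than one definition to choose from.

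**Working it through.** The plan states no figure on this point to reproduce, so the check is mainly a comparison of the text.

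**1. Reference points, side by side.**

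| Place | Baseline or reference |
|---|---|
| SAP 5.1, general rule | infusion start (serelaxin); randomization (SOC) |
| SAP 4.1, EQ-5D collection | randomization, both arms |
| SAP 5.2, EQ-5D model | randomization |
| SAP 5.3, blood-pressure decrease event definition | reading just before infusion |
| SAP 5.3, systolic pressure summary by event status | randomization |
| Protocol 9.5.4, EQ-5D change | score at screening, with the baseline value as covariate |

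For EQ-5D alone there are three reference points.

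**2. Can an assessment fall in the gap?** Protocol Table 6-1 puts the physician assessment, EQ-5D, an IRT contact and the start of study drug in one column, End of Screening/Baseline, with no order stated. So it can. No efficacy assessment is scheduled there for serelaxin alone. The only extra scheduled pre-infusion measurement is blood pressure and heart rate (protocol 6.5.2).

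**3. A hypothetical patient.** Suppose orthopnea is graded 1 before randomization and 0 forty minutes later, before any infusion.
- On SOC the second grade is post-baseline, so the patient is a responder at about 40 minutes.
- On serelaxin the second grade precedes baseline under SAP 5.1. If it is taken as the baseline value, the exclusion rule removes the patient from the orthopnea analysis.
- If the grades are 2 and then 1, the SOC patient responds at 40 minutes, while the serelaxin patient must still reach 0.

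The clock starts at randomization in both arms. Improvement before infusion can therefore be absorbed into a serelaxin baseline but counted as response on SOC.

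**4. Patients never infused.** Protocol 5.5.1 and 5.5.5 foresee serelaxin-arm patients who get no drug and stay in follow-up. They remain in the FAS if not mis-randomized. The baseline sentence gives them no baseline; only the post-baseline sentence covers them.

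**5. Which analyses use the baseline value.**
- Used: sign/symptom response, with the accompanying change scores, and EQ-5D change and covariate.
- Not used: the primary endpoint; persistent signs or symptoms, which SAP 4.1 defines by IV therapy at the time point; and renal deterioration, laboratory change and between-arm vital-sign change, all taken from screening.

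**6. Size, on assumptions only.** The documents do not say how often an assessment falls in the gap, or how fast scores move. Let p be the assumed share improving by at least 1 point within 6 hours at a constant rate, and d the gap in hours. The share whose score would move within the gap is 1 − (1 − p)^(d/6).

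| p | d = 0.5 h | d = 1 h |
|---|---|---|
| 20% | 1.8% | 3.7% |
| 30% | 2.9% | 5.8% |
| 50% | 5.6% | 10.9% |

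These shares apply only to patients actually assessed at infusion start. They do not estimate how many patients are affected.

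**The case against.** The best reply is the nominal-time rule. Both arms share one nominal baseline visit, so a record from that visit can be read as baseline in either arm whatever its clock time. SAP 5.1 defines a baseline moment and does not say which value is selected. On that reading the asymmetry may never reach the data.

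This stands in part: the asymmetry is permitted, not planned. It is not a full answer. Symptom response is a time-to-event analysis on actual times, with event and eligibility set by the baseline value. Elsewhere the nominal rule competes with a baseline defined by date and time, which leaves two readings.

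A reader might also infer more than the documents support:
- *That only serelaxin patients can have a baseline obtained after allocation.* Protocol 6.6.4 and SAP 4.1 let a patient in either arm give the EQ-5D baseline by recall on Day 2. The asymmetry concerns contemporaneous values.
- *That every serelaxin patient is affected*, which would be 3,183 × 2/3 = 2,122. Never-infused patients have no infusion-start baseline, and among the rest only those with a record in the gap could be affected.
- *That the gap measures the bias.* 30/360 = 8.3% and 60/360 = 16.7% are ratios of times to the 6-hour assessment, not shares of patients or effect sizes.
- *That the censoring rules in SAP 5.2 add to the conflict.* They also gloss baseline as randomization, but SAP 5.1 already ties time-to-event analyses to randomization.
- *That the rule favours serelaxin.* The mechanism in the hypothetical case works against it, and knowledge of allocation could work either way.

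**Conclusion.** The point holds as a defect of definition with limited reach. SAP 5.1 states an arm-dependent efficacy baseline in an open-label trial. It is inconsistent with the SAP's own EQ-5D and systolic pressure text and with protocol 9.5.4. It permits, on serelaxin only, a contemporaneous post-allocation symptom or EQ-5D value to act as baseline.

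The reach is the sign/symptom response analyses and the EQ-5D change analyses, which are secondary and carry no multiplicity adjustment. The primary test, its significance level, its time origin and the sample size are unaffected. The number of patients affected and the direction of bias cannot be determined from the documents. The conclusion rests on reading SAP 5.1 as written and on the schedule leaving the order of events at the baseline visit open. It should be corrected before database lock, but it does not threaten the main result.

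**What to change.** 1. For efficacy measures in both arms, including serelaxin patients never infused, define baseline as the last value at or before randomization. Treat values between randomization and infusion as post-baseline.
2. For EQ-5D, accept the Day 2 recalled baseline in both arms where no earlier value exists, and add a sensitivity analysis excluding recalled values.
3. Keep the pre-infusion reading only as the reference for serelaxin blood-pressure and infusion safety summaries.
4. Bring SAP 5.1, the EQ-5D model in SAP 5.2, the systolic pressure summary in SAP 5.3 and protocol 9.5.4 into agreement.

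The cost is a short SAP revision and an aligned protocol reference, with no new data collection. The downside is that a few patients in either arm, whose only baseline-visit assessment was made after randomization, lose their baseline for that measure. Their number should be reported by arm.

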remainder of the 48-hour study drug administration. Serelaxin administration will be permanently discontinued at any time if in 2 consecutive measurements; 15 minutes apart, systolic blood pressure is reduced to <100 mmHg.

Table 5-2 describes the actions required for a systolic BP decrease during the period of study drug infusion, which must be strictly followed.

Table 5-2 Dosing adjustment of study drug administration in the event of systolic BP decrease through completion of study drug infusion

Changes in systolic BP during infusion*	Adjustments of study drug administration
Decrease >40 mmHg from pre-treatment (i.e., measured just before the immediate start of study drug infusion), but systolic BP remains ≥ 100 mmHg	Reduce the infusion rate by half for the remainder of the study drug administration, i.e., reduce infusion rate from 10 mL/hour to 5 mL/hour for the remainder of 48-hour infusion
Decrease in absolute value of systolic BP to <100 mmHg	Permanently terminate study drug infusion

* These systolic BP values should be confirmed by two measurements taken 15 minutes apart.

In addition, dosing may be discontinued at any time at the discretion of the investigator. Reasons the investigator may discontinue study drug administration include, but are not limited to, serious or intolerable AEs suspected to be related to study drug. If dosing is discontinued for BP decreases, or any safety reasons, it should not be restarted. Re-administration of study drug once terminated for safety reasons is not allowed. The total time from initiation of study drug infusion to completion must not exceed 48 hours. In the event that study drug administration is discontinued, regardless of the reason, the patient will continue to be followed at all study visits defined in the protocol. These changes in study drug dose must be recorded on the Dosage Administration Record eCRF.

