9.3 Treatments

9.3.1 Investigational Treatment

Overall study treatment administration details will be summarized for the FAS and the Safety population in the serelaxin arm only. This will include time from presentation to randomization (in hours), time from randomization to study treatment initiation (in hours), time from presentation to study treatment initiation (in hours), study treatment administered (yes/no), reason study treatment not administered, actual treatment received, and the number of days study treatment infused (one or two). The duration of study treatment administration (in hours) and the total volume of study treatment administered (estimated from the total time and rate of infusion) will be summarized. In addition, the number of subjects whose study medication dose was lowered or discontinued prematurely, and the reasons for discontinuation, will be summarized. Logistic regression models will be fitted considering demographics and anamnestic factors in order to identify main predictors for drug discontinuation. Odds ratio and 95% confidence intervals will be provided.

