2.4. STUDY DRUG AND DOSING

Serelaxin is administered according to a weight-range adjusted dosing regimen at a nominal dose of 30 µg/kg/day, as a continuous intravenous infusion for 48 hours.

The study drug is provided as a 1 mg/mL solution in 6 mL vials (with 3.5 mL fill). For the randomized patients to receive the study drug infusion, it can be withdrawn from the vials contained in the kits, injected into a 250 mL intravenous bag of 5% dextrose solution and then infused through a dedicated IV line or port, using compatible tubing, infusion filters and IV bags according to instructions in the Pharmacy Manual.

Each study site is supplied by Novartis with investigational treatment in kits containing 1 vial of serelaxin each, enough study drug for 24 hours of infusion (for all patients < 115 kg in body weight). At randomization time, the IRT specifies the first package of investigational treatment to be dispensed to the patient; to receive the study drug for the second 24 hours of infusion, the investigator's staff contacts the IRT again and requests a second kit (for patients randomized to serelaxin only). In case the subject is ≥ 115 kg in body weight, two study drug kits are assigned via IRT for each 24 hour of infusion.

Statistical Analysis Plan

Sponsor: NOVARTIS

Protocol number: CRLX030A3301

Table 2.4-1: Weight-range adjusted dosing regimen of serelaxin

Body weight (kg)	Serelaxin (mg)	Volume of serelaxin to be added to 250 mL IV bag of sterile 5% dextrose for intravenous infusion over a period of 24 hours
40-59 kg	2.0 mg	2.0 mL
60-74 kg	3.0 mg	3.0 mL
75-114 kg	3.5 mg	3.5 mL
115-160 kg	5.5 mg	5.5 mL (2 vials needed)

All kits of investigational treatment assigned by the IRT will be recorded in the IRT.

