Due to the potential risk of hypotension, blood pressure is monitored regularly during the administration of study drug. If at any time during dosing, the subject's systolic blood pressure decreases by > 40 mm Hg from just before the study drug infusion but is ≥ 100 mmHg in 2 consecutive measurements 15 minutes apart, serelaxin infusion rate is decreased by 50% for the remainder of the 48 hour study drug administration. Serelaxin administration is permanently discontinued at any time if in 2 consecutive measurements, 15 minutes apart, systolic blood pressure is reduced to < 100 mmHg. In addition, dosing may be discontinued at any time at the discretion of the investigator. Reasons the investigator may discontinue study drug administration include, but are not limited to, serious or intolerable adverse events (AEs) suspected to be related to study drug. If dosing is discontinued for hypotension or any safety reasons, re-administration of study drug is not allowed. For non-safety reasons (problems with the infusion line, etc.), dosing may be interrupted once for each patient for up to 1 hour. Time from initiation of study drug infusion to completion must not exceed 48 hours (i.e., if the infusion is interrupted or delayed, it must be terminated after 48h from the start, regardless of the actual infusion time). In the event that study drug administration is discontinued for any reason, the patient will continue to be followed at all study visits defined in the protocol.

No additional treatment beyond investigational treatment is requested for this trial. All patients are required to receive standard of care background HF management during the study, according to local guidelines/international standards. This treatment can include but is not limited to intravenous and/or oral diuretics, angiotensin-converting enzyme (ACE) inhibitors/angiotensin receptor antagonists, β blockers and aldosterone receptor antagonists, etc.

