- Total volume of study treatment administered (mL) for patients in the serelaxin arm only is estimated from the duration of infusion in hours and the corresponding rate of infusion in mL/hr. It will be computed as the sum of the reported total volumes of study treatment throughout the study.
- Duration of study treatment administration (hours) for patients in the serelaxin arm only. It will be presented as elapsed hours and minutes +1 minute from the start to the end of infusion; any temporary treatment interruptions will not be detracted. Number of days study treatment infused: the following discrete categories will be computed and described, <1 day (i.e., <1440 minutes), between 1 and 2 days (i.e., >=1440 and <=2880 minutes) and >2 days (i.e., >2880 minutes). The continuous variable duration of study treatment infusion in days and in hours will be summarized as well.
- Any dose reduction (yes/no) and reason for dose reduction for patients in the serelaxin arm only. A dose reduction is defined as a rate of infusion lower than the rate of infusion reported in the previous infusion record. Reason for dose reduction will be summarized and percentages will be computed on total number of dose reduction. Number and percentages of patients who reported any dose reduction by reason for dose reduction will be provided.
- Number of patients for whom study medication dose was discontinued prematurely, and the reason for discontinuation for patients in the serelaxin arm only. Patients who

	Statistical Analysis Plan
	Sponsor: NOVARTIS Protocol number: CRLX030A3301

discontinued prematurely the study drug are defined as patients with at least one dose infusion and “Subject Status” on the eCRF page “Treatment Completion” different from ‘Completed’. The “Subject Status” will be summarized as well.

- A listing of patients with actual treatment received different from randomized treatment will be provided for the Safety set only for both arms.

Logistic regression models will be fitted considering demographics and anamnestic factors in order to identify main predictors for study drug discontinuation. Odds ratio and 95% confidence intervals will be provided.

Univariate regression models will be fitted considering as factors the following variables: age, gender, BMI at screening. Moreover, a multivariate regression model will be fitted considering all the factors above mentioned and selected with a stepwise method.

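### The infusion-duration classes in SAP 5.1 are not shifted for the added minute, so an exact 48:00 infusion is tabulated as more than 2 days

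*SAP*

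**What the plan says.** The rule and the classes stand in one bullet of SAP 5.1, under Investigational treatment. The bullet concerns "Duration of study treatment administration (hours) for patients in the serelaxin arm only". Duration is derived as follows: "It will be presented as elapsed hours and minutes +1 minute from the start to the end of infusion". Interruptions stay in: "any temporary treatment interruptions will not be detracted". The number of days infused is then given in classes. The first is below 1440 minutes; the other two are "between 1 and 2 days (i.e., >=1440 and <=2880 minutes) and >2 days (i.e., >2880 minutes". The bullet ends by promising a continuous summary of duration in days and in hours. The table is produced for the FAS and the Safety set.

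The planned administration is "as a continuous intravenous infusion for 48 hours" (SAP 2.4). The same figure is the ceiling. Protocol 5.5.5 states: "The total time from initiation of study drug infusion to completion must not exceed 48 hours". SAP 2.4 repeats it: "Time from initiation of study drug infusion to completion must not exceed 48 hours". For this summary, Protocol 9.3.1 foresaw only "the number of days study treatment infused (one or two" as values, with no category above two days.

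**The concern.** The cut-points are 24 and 48 hours expressed in minutes. The variable being cut is one minute longer than the elapsed time. The upper cut-point therefore falls just below the value computed for an infusion that ran exactly as planned.

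This is more than a remote edge case, because several rules lead towards a start-to-stop time of exactly 48:00. It is the planned duration. Under SAP 2.4, an interrupted or delayed infusion must end 48 hours after its start whatever the actual infusion time. A patient whose rate is halved continues for the rest of the 48-hour administration (Protocol 5.5.5).

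What is at stake is the meaning of one row in the exposure table. The row for more than 2 days would combine infusions that ended exactly on time with infusions that ran past 48 hours, and its count could not separate them.

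**Working it through.** **Inputs**
- Derived duration (SAP 5.1): D = (end − start) + 1 minute, with interruptions not subtracted.
- Classes (SAP 5.1): D < 1440; 1440 ≤ D ≤ 2880; D > 2880 minutes.
- Planned and maximum start-to-stop time (SAP 2.4, Protocol 5.5.5): 48 hours.

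**The plan's own cut-points.** 24 × 60 = 1440 and 48 × 60 = 2880. Both reproduce exactly as whole days in minutes, so neither contains the added minute.

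**Applying the rule on each side of both cut-points**

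| Recorded start to stop | Elapsed (min) | Class without the added minute | D = elapsed + 1 (min) | Class under the SAP rule |
|---|---|---|---|---|
| 23:58 | 1438 | <1 day | 1439 | <1 day |
| 23:59 | 1439 | <1 day | 1440 | 1 to 2 days |
| 24:00 | 1440 | 1 to 2 days | 1441 | 1 to 2 days |
| 47:58 | 2878 | 1 to 2 days | 2879 | 1 to 2 days |
| 47:59 | 2879 | 1 to 2 days | 2880 | 1 to 2 days |
| 48:00 | 2880 | 1 to 2 days | 2881 | >2 days |
| 48:01 | 2881 | >2 days | 2882 | >2 days |

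Exactly two recorded durations change class: 23:59 and 48:00. For 48:00 the derived value is 2881/60 = 48.017 hours, or 2881/1440 = 2.0007 days.

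**Interrupted infusions.** SAP 2.4 allows one interruption of up to 1 hour for non-safety reasons. Take a patient interrupted for the full hour and stopped at 48:00 from the start. Actual infusion is 2880 − 60 = 2820 minutes (47 hours). Because the interruption is not subtracted, D is still 2881 and the patient is counted as more than 2 days.

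**Checking the corrections.** Classifying on elapsed time gives the third column of classes in the table (without the added minute). Keeping D and using <1441, 1441 to 2881 and >2881 gives the same result: 23:59 (1440) is <1 day, 24:00 (1441) is 1 to 2 days, 48:00 (2881) is 1 to 2 days, and 48:01 (2882) is >2 days.

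**The case against.** **The classes may be meant for plain elapsed time.** The added minute is attached to how duration is presented, while the classes are said to be computed, and cut-points at whole multiples of 1440 suit unadjusted elapsed time. This is possible, but the bullet defines no other duration and does not exempt the classes. Elsewhere the SAP compares a difference plus 1 minute directly with a round limit (120 hours in Table 5.2-2, 336 hours in Table 5.2-4). The reading used here is the natural one, though not certain. If the other was intended, the SAP still needs to say so.

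**The class is not a compliance flag.** A reader might infer that the class above 2 days exists to report breaches of the 48-hour limit. The documents do not say this. The class coincides numerically with the limit, but SAP 5.1 presents it only as a description of days infused. Protocol deviations are identified separately before database lock, and no row of SAP Table 3-1 uses these classes or the 2880-minute limit. This objection stands.

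**Over-runs are not concealed.** The continuous summary in the same bullet includes quartiles and the maximum. A material over-run would appear in the maximum and, if common, in the upper quartile. What is lost is the count of over-runs in the categorical row. This objection also stands.

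**Conclusion.** The point holds as an inconsistency between a derivation rule and its class limits. If the classes use the derived duration, every infusion recorded as exactly 48:00 is counted as more than 2 days, and every one recorded as 23:59 as 1 to 2 days. Records of 47:59 or shorter are unaffected at the upper limit.

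The number of patients involved cannot be obtained from the documents. A reader might assume that 48:00 is the most frequent record and apply a share to the planned serelaxin arm of about 2,122 (two thirds of 3,183). Neither step is supported. The documents give no distribution of recorded durations. That base also includes patients who never start serelaxin or stop early, whereas SAP 5.1 takes percentages over patients with non-missing information. An exact 48:00 record is plausible because it is the planned duration; its frequency is unknown.

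The consequence is small: one descriptive table, in the serelaxin arm only, for the FAS and the Safety set. The primary and secondary tests do not use these classes. Analysis-set membership does not depend on them, and premature discontinuation is taken from the subject status on the treatment completion page. This is a minor correction, but the count as specified would be wrong.

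**What to change.** Amend the bullet in SAP 5.1 in one of two equivalent ways:
- Classify on elapsed time (end − start, without the added minute) and keep <1440, 1440 to 2880 and >2880 minutes.
- Keep the added minute and change the classes to <1441, 1441 to 2881 and >2881 minutes.

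In either case, add a sentence stating which duration is categorized. The first option is easier to read, because the limits remain whole days. Under either option the top class contains only start-to-stop times longer than 48:00.

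The cost is one line in the SAP and the matching line in the table specification. No data collection, dosing rule, analysis set or test is touched.
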